This study will recruit 15 people with chronic and stable stroke (>6 months) who are interested in ambulation training using a powered exoskeleton. This study will be conducted at the James J. Peters VA Medical Center (JJPVAMC) therefore recruitment training and testing in this project will require participants to travel to this medical center in the Bronx, NY. The following criteria will be employed for participation:

Inclusion Criteria:

1. Males and females between 18 and 89 years old;
2. Hemiplegia or hemiparesis due to stroke (>6 months);
3. Able to walk between 0.15-0.75m/s
4. Self-reported limitations to mobility and walking activities due to paretic side knee stiffness and loss of range of motion;
5. Weight under 250lbs
6. Desire to increase daily activity levels; and
7. Able and willing to commit to participation and follow directions and communicate basic needs.

Exclusion criteria:

1. Neurological paralysis causing an inability to stand, weight bear or take stepping movements;
2. Fixed contractures resulting in limited range of motion in the hip, knees, or ankles that prevent sitting, standing, walking, and/or squatting activities;
3. Modified Ashworth Scale for spasticity greater than 3 in the lower limbs
4. Able to walk at a normal walking speed (1.4 m/s, 3.2 mph) or better during the 6MWT;
5. Anthropometric incompatibility with the device
 - a. Femur length less than 36 cm or greater than 45 cm;
 - b. Upper thigh circumference less than 55 cm or greater than 75 cm;

- c. Lower thigh circumference less than 27 cm or greater than 40 cm;
- d. Calf circumference less than 33 cm or greater than 49 cm;
- e. Ankle circumference less than 27 cm or greater than 40 cm;
- f. Shin length less than 26 cm;
- g. Waist circumference less than 71 cm or greater than 107 cm;
- 6. Any medical complication or co-morbidity as judged by the study physician to be contraindicated for wearing the device or walking (e.g., cardiovascular disorders, pressure ulcers, open wounds, lower limb vascular disorders, or other medical conditions); and
- 7. Pregnant or planning to become pregnant (Female participants).

A subset of participants will have MEP recordings using as a result of PNS, TSCS and TMS. The inclusion criteria is the same as previously described. The following is the additional exclusion criteria.

Exclusion criteria:

- 1. History of seizures, brain tumor, brain surgery, or brain abscess;

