- 2. Use of medications that significantly lower seizure threshold, such as amphetamines, neuroleptics, dalfampridine, and bupropion;
- 3. History of moderate or severe head trauma (loss of consciousness for greater than one hour or evidence of brain contusion, hemorrhage or depressed skull fracture on prior imaging); Recent (within the last 5 years) brain injury with definite loss of consciousness;
- 4. History of implanted brain/spine/nerve stimulators, aneurysm clips, ferromagnetic metallic implants, or cardiac pacemaker/defibrillator;
- 5. Significant coronary artery or cardiac conduction disease;
- 6. History of bipolar disorder; Active psychosis;
- 7. History of suicide attempt;
- 8. History of migraines or reoccurring headaches;
- 9. Heavy alcohol consumption (greater than equivalent of 5 oz of liquor) within previous 48 hours;
- 10. Open skin lesions over the face, back, legs, or feet;
- 11. Unsuitable for study participation as determined by study PI.

In this study, special classes of participants such as pregnant women, prisoners, institutionalized individuals, or other populations that may be considered vulnerable will be excluded from this study except for economically and educationally disadvantaged persons. There are Veterans and military members who are economically, educationally or socially disadvantaged individuals and they will be given the opportunity to participate in this research project. We will not try to identify those who are economically and educationally disadvantaged as the details of this study would not influence their decision to participate. These disadvantaged persons will be given the same treatment as individuals who are not considered to be vulnerable.

Recruitment Methods

Recruitment for this study will comply with the standards of VHA Handbook 1200.05 and is planned to be performed in the following ways:

- Referrals from primary care physicians.

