The device itself could malfunction. The device has built-in mechanical stops to limit the devices ability to move through abnormal ranges of motion. In addition, the activities that will be performed with the device will be performed by trained research personnel to monitor device function during use. Participants that use the device in the home environment will have had many hours of prior training to use the system and will be trained to handle any device malfunction.

The DXA scans involve ionizing radiation. We estimate all of these DXA measurements combined will sum up to less than 35 μ Sv of absorbed radiation. This measurement is minimal even when compared to a routine chest x-ray which has an approximate dose of 60 μ Sv. In addition, the average person in New York City receives approximately 3000 μ Sv/year. Therefore, you would have to have all these tests done 100 times to receive an equivalent dose.

Scan Type	Entrance Dose	Effective Dose	Scan Time
Total Body	6 μ Gy	8.62 μ Sv	739 sec
Dual Femur	329 μ Gy	12.3 μ Sv	212 sec
Knee	34 μ Gy	2.0 μ Sv	54 sec

This research may have unknown effects on an unborn child. For female born participants, the study should not be performed during pregnancy (a pregnancy test may be requested). You also agree to avoid becoming pregnant during the study.

There always exists the potential for loss of private information; there are procedures in place to minimize this risk.

There may also be potential risks that are unknown.

Additional risks related to the additional pilot study involving brain, spine and peripheral nerve stimulation:

TMS carries several potential risks. Most of these risks are much greater during application of repetitive TMS, or rTMS (defined as pulses given at a frequency of 1 per second or more frequently), which will not be conducted in this study. There is a small risk of seizure or “convulsive syncope” (fainting with seizure-like movements).

- Before you begin participation in the Study, we will screen you for seizure risk, such as history of prior brain injury, or taking certain medications that raise the risk of seizure. If your seizure risk is too high, you will not be able to participate in the Study.
- Furthermore, the applied stimulus intensity will be kept below 200% of the motor threshold for each muscle. This intensity and pulse frequency fall far within the recommended safe guidelines delineated by TMS experts.

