All procedures take place within the JJPVAMC, where there is access to all forms of life-support equipment, medications, and medical personnel. In the unlikely event of a seizure during this study, you should be aware of the implications a seizure could have on your future employment, insurance and eligibility to drive. Since such an event would be considered a response to the procedure and not an underlying disease, a letter documenting that this event does not indicate any underlying disease that could affect your employability, driver's license, or health/life insurability will be provided. If there are any symptoms of dizziness or lightheadedness, which could potentially be warning signs of convulsive syncope, we will halt the procedure immediately, investigate and take steps to end the symptoms. If you feel as though you will pass out. We will lie you down and elevate your legs. Those with previous history of syncope will be assessed for eligibility.

There is a possible but unlikely risk of TMS triggering psychotic or manic symptoms in participants with bipolar depression. This is a very small risk – it is not clearly above the natural rate for these types of symptoms to occur in participants with depression. You will not be able to participate in the study if you have a history of bipolar disease, active psychotic symptoms, or history of suicide attempt.

TMS pulses generate loud auditory clicks. Risk of hearing changes due to the ‘click’ of the stimulator will be minimized by using earplugs during the experiment. Individuals who complain of hearing loss, ringing in the ears (tinnitus), or ear pressure following completion of TMS will be referred to the appropriate medical care.

While individuals with cochlear implants will be excluded, pre-existing hearing issues will be assessed for eligibility.

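### The stimulation risk text attributes a seizure to the procedure before any event and promises an unconditional letter, although every stimulated participant has had a stroke

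*Combined protocol and SAP*

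**What the plan says.** The statement is in section 04 (Human Subjects), under Potential Risks, in the part on brain, spine and peripheral nerve stimulation. It opens: "In the unlikely event of a seizure during this study, you should be aware of the implications a seizure could have" for employment, insurance and driving. It continues: "Since such an event would be considered a response to the procedure and not an underlying disease, a letter" will follow, "documenting that this event does not indicate any underlying disease that could affect your employability", "driver's license, or health/life insurability will be provided".

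Three other places bear on it:

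- **Inclusion criterion 2** of the main study requires "Hemiplegia or hemiparesis due to stroke (>6 months" since the event).
- **The stimulation subset** is introduced with "A subset of participants will have MEP recordings using as a result of PNS, TSCS and TMS". The next sentence gives it the same inclusion criteria as the main study, and a list of additional exclusions follows.
- **The TMS risk text**, shortly before the seizure statement, says "we will screen you for seizure risk, such as history of prior brain injury" or use of certain medications. Anyone whose seizure risk is too high is not to take part.

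**The concern.** The text fixes a causal conclusion in advance. It says that a seizure comes from the procedure and not from disease, and it commits the study to putting the second half of that in writing. In a sample without brain disease such a statement might be defensible. Here the entry condition is itself a disease of the brain, and the same risk text accepts that earlier brain injury bears on seizure risk.

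What is at stake is the truth of a document that a participant may rely on for driving, employment or insurance. If a seizure did reflect the stroke lesion, the letter would say otherwise, and the participant could be wrongly reassured. Because the promise is made directly to the participant, the investigator might also be unable to honour it honestly once the event had been looked into.

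**Working it through.** No arithmetic applies. The plan attaches no figure to this point and gives no seizure rate. The check is to set the statements side by side.

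1. **Is the attribution conditional?** No. The sentence moves directly from the occurrence of a seizure to its cause. It sets no limit on the time since stimulation and no prior evaluation. Its literal scope is a seizure at any point in the study. Its place in the stimulation text suggests a seizure around stimulation. The point holds on either reading.

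2. **Is the letter conditional?** No. It is simply to be provided. The Data and Safety Monitoring Plan makes the principal investigator responsible for the accuracy and completeness of event reports, but nothing there or in the risk text makes the letter depend on an assessment.

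3. **Who is covered?** Everyone stimulated. The subset has the main study's inclusion criteria, and criterion 2 requires a stroke. So every person to whom the promise is made has had one.

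4. **Do the additional exclusions remove the difficulty?** They narrow it. They take out people with previous seizures, certain other brain conditions or operations, drugs that lower the seizure threshold, significant head trauma, and "Recent (within the last 5 years) brain injury with definite loss of consciousness". They do not take out stroke, and cannot, because it is required for entry.

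5. **Does the protocol recognise brain injury as relevant to seizure?** Yes, in the screening statement quoted above. Before stimulation, earlier brain injury is a reason for caution. After a seizure, disease is ruled out as the cause without inquiry.

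6. **How are lesser events handled in the same text?** Dizziness or lightheadedness leads to a halt and investigation. A significant change in blood pressure or oxygen level with symptoms leads to cessation and medical evaluation. For the seizure itself, the cause is already given.

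From steps 1 to 3, the letter would go, without assessment, to a person with a known stroke. From steps 4 and 5, the protocol's own safeguards do not exclude that stroke as a contributor. The content of the letter therefore cannot be known to be true when the promise is made.

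**The case against.** The best case against the point is that this is consent-style wording about a rare event, set among real safeguards. Repetitive TMS is not used, stimulus intensity is capped, people with previous seizures are excluded, and the risk of seizure is described as small. Emergency personnel are called for a serious event, and the primary care physician is told of findings that may affect health. The letter replaces none of this. All of that stands and limits the weight of the point. It does not make the letter's content depend on what is found.

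Four stronger readings are tempting, and the documents do not support them.

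- **That the letter certifies the participant free of disease.** It speaks only to what the event indicates about disease affecting work, driving or insurance. It does not deny the stroke.
- **That the seizure-risk screen must exclude everyone or distinguish no one.** Prior brain injury is given as one example within a graded decision on whether risk is too high, and a factor shared by all can still vary in degree. The documents never expressly call stroke a prior brain injury, and the brain-injury exclusion sits within the item on head trauma. Whether the qualifying stroke counts in the screen would be useful to know, but it is a clarification and not part of this point.
- **That the safety record is distorted.** Event handling is set out separately: a standard side-effect form after each TMS session, recording of all adverse events with submission to the IRB, review by the principal investigator, and annual IRB review. Nothing says that the seizure sentence overrides these. Attributing a seizure to the procedure also counts it against the procedure and so hides no harm. The procedure meant here is stimulation, not the exoskeleton.
- **That the problem affects 100% of the subset at every stimulation visit.** That counts people exposed to the wording. The letter is triggered only by a seizure.

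**Conclusion.** The point holds in a narrow form. The advance attribution and the unconditional letter do not fit a sample in which everyone has had a stroke, because whether the letter is true depends on an assessment that the text does not require.

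The size is not numerical. The promise reaches every member of a subset of unstated size, drawn from the 15 planned participants, and takes effect only if a seizure occurs. Sample size, endpoints, analyses and study procedures are untouched. It merits correction because the possible consequence, an unsupported statement on driving and employment, is serious for the person concerned and the correction is cheap.

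The conclusion rests on the plain meaning of stroke as damage to the brain. It uses no outside seizure rate and assumes none.

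**What to change.** Reconcile the seizure statement under Potential Risks with inclusion criterion 2 and with the seizure-risk screening statement. Remove the attribution made in advance and the unconditional promise, so that what any letter says follows from the assessment of the individual event. The study physician and the IRB should settle the wording. No clinical rule is proposed here.

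The cost is a wording change to the protocol and consent form with IRB review, and a less reassuring statement to participants.
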